## 7.1.4 Definition of a Serious Adverse Event

An SAE is any untoward medical occurrence regardless of the grade that:

- results in death,
- is life-threatening,
- requires inpatient hospitalization or prolongation of existing hospitalization,
- results in persistent or significant disability/incapacity, or,
- is a congenital anomaly/birth defect.

Important medical events that may not be one of the above may be considered an SAE by the Investigator when, based upon appropriate medical judgement, are considered clinically significant and may jeopardize the participant, or may require medical or surgical intervention to prevent one of the outcomes listed above.

"Life-threatening" means that the participant was at immediate risk of death from the experience that, had it occurred in a more serious form might have caused death.

A congenital anomaly in an infant born to a mother who was exposed to the IP during pregnancy is considered an SAE. However, a newly diagnosed pregnancy in a patient that has received the IP is not considered an SAE unless it is suspected that the IP interacted with a contraceptive method and led to the pregnancy. Procedures for notification of pregnancies and follow-up are described in Section.

#### 7.1.5 Clinical Laboratory Abnormalities and Other Abnormal Assessments as Adverse Events and Serious Adverse Events

Abnormal laboratory findings (e.g., clinical chemistry, hematology, and urinalysis) or other abnormal assessments (e.g., ECG, X-rays, and vital signs) per se are not reported as AEs. However, those abnormal findings that are deemed **clinically significant** or are associated with signs and/or symptoms must be recorded as AEs if they meet the definition of an AE (and recorded as an SAE if they meet the criteria of being serious) as described previously. Clinically significant abnormal laboratory or other abnormal findings that are detected after consent or that are present at the time of consent and worsen after consent are included as AEs (and SAEs if serious).

The Investigator should exercise his or her medical and scientific judgment in deciding whether an abnormal laboratory finding or other abnormal assessment is clinically significant. Usually, the abnormality should be associated with a clinically evident sign or symptom, or be likely to result in an evident sign or symptom in the near term, to be considered clinically significant. A clinically significant laboratory abnormality in the absence of clinical symptoms may jeopardize the participant and may require intervention to prevent immediate consequences. For example, a markedly low serum glucose concentration may not be accompanied by coma or convulsions, yet be of a magnitude to require glucose administration to prevent such sequelae.

#### 7.2 Documenting Adverse Events

Any AE occurrence (spontaneously volunteered and enquired for, as well as observed AEs) during the study must be documented in the patient's medical records in accordance with the Investigator's normal clinical practice and on the AE page of the eCRF. SAEs that occur during

the study must be documented in the patient's medical record, on the AE eCRF, and on the SAE form.

The Investigator should attempt to establish a diagnosis of the event based on the signs, symptoms, and/or other clinical information. In such cases, the diagnosis should be documented as the AE (and SAE if serious) and not the individual signs/symptoms.

If a clinically significant abnormal laboratory finding or other abnormal assessment meets the definition of an AE, then the AE eCRF page in the REDCap database must be completed as appropriate. In addition, if the abnormal assessment meets the criteria for being serious, the SAE form must also be completed. A diagnosis, if known, or clinical signs or symptoms if the diagnosis is unknown, rather than the clinically significant laboratory finding or abnormal assessment, should be used to complete the AE/SAE page. If no diagnosis is known and clinical signs or symptoms are not present, then the abnormal finding should be recorded. If an SAE report is completed, pertinent laboratory data should be recorded on the SAE form, with baseline values and copies of laboratory reports.

The SAE page should be completed as thoroughly as possible and signed by the Investigator before transmittal to Oncolys BioPharma Inc at [contact].

It is very important that the Investigator provide an assessment of the causal relationship between the event and the IP at the time of the initial report, as this will be useful for submissions to regulatory authorities.

#### 7.2.1 Recording of Adverse Events

All adverse events will be recorded on a patient specific AE log after W1D1 and entered onto REDCap. The AE log will be maintained by the research staff and kept in the patient's research chart.

# 7.2.2 Reporting of AE to WCMC IRB

All adverse events will be recorded on a patient specific AE log after Day 1. The AE log will be maintained by the research staff and kept in the patient's research chart.

# 7.2.3 Follow-up of Adverse Events and Serious Adverse Events

In this study, non-serious AEs will be reported in all participants from Treatmet 1. Non-serious AEs reported from the time of consent to injecting on Day 1 will be recorded as medical history. Serious adverse events (SAEs) will be reported in all patients (enrolled and not enrolled) from the time of consent. Study procedure-related AEs will be evaluated specifically from the time of consent until the administration of OBP-301. Treatment-emergent AEs will be evaluated from the time of injecting with IP until the Final Visit. The Investigator is responsible to ensure that follow-up includes any supplemental investigations as may be indicated to elucidate as completely as practical the nature and/or causality of the AE/SAE. This may include additional laboratory tests or investigations, histopathological examinations, or consultation with other health care professionals.

All non-serious AEs that are ongoing at the Final Visit will be marked as ongoing on the AE eCRF page in the REDCap database.

All SAEs that are ongoing at the Final Visit must be followed until resolution, until the condition stabilizes, until the event is, in the opinion of the Investigator, stabilized or determined to be chronic, or until the participant dies or is lost to follow-up. SAEs that occur after the Final Visit, that are thought to be related to the administration of OBP-301, should be reported to Oncolys BioPharma Inc. or designee.

If a participant is withdrawn because of an AE, the Investigator must arrange for the participant to have appropriate follow-up care until the AE is resolved or has stabilized. Unresolved AEs will be followed until the last scheduled follow-up visit or until the Investigator and Medical Monitor determine that further follow-up is no longer indicated. Oncolys BioPharma Inc. may request that the Investigator perform or arrange for the conduct of supplemental measurements and/or evaluations. If a participant dies during participation in the study or during a recognized Follow-up Period, Oncolys BioPharma Inc. should be provided with a copy of any post-mortem findings, including histopathology.

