Investigational Product Administration:	OBP-301, the investigational product (IP) is formulated in 20 mM Tris pH 8.0, 25 mM NaCl with 2.5% glycerin, USP by volume. OBP-301 will be injected into the target tumor lesions.
Planned Patients:	41 patients in total for both stage 1 and 2, to achieve 37 evaluable patients.
Participant Selection	Inclusion Criteria:
Criteria:	Patients who meet all of the following criteria will be considered for inclusion in the study:
	
 
Be willing and able to provide written informed consent for the trial.
 
Be ≥18 years of age on the day of signing the informed consent.
 
Have an Eastern Cooperative Oncology Group (ECOG) performance status of 0-2.
 
Have histologically or cytologically confirmed advanced or metastatic gastroesophageal adenocarcinoma, at least 1 cm in size and amenable to intratumoral injection.
 
Patient must have received at least 2 line of systemic therapy for advanced disease.
 
Tumor must be PD-L1 positive, as defined by a combined positive score (CPS).
 
Have one or more measurable lesions based on iRECIST.
 
Be willing to provide tissue; newly obtained biopsy specimens or formalin-fixed, paraffin-embedded (FFPE) block specimens.
 
Female subjects of childbearing potential have a negative urine or serum pregnancy test within 7 days prior to enrollment. If the urine test is positive or cannot be confirmed as negative, a serum
 

10.	pregnancy test will be required. If a serum pregnancy test is required it can be performed on the same day as the urine pregnancy test. The serum pregnancy test must also be completed 7 days prior to enrollment. And male / female subjects of childbearing potential must agree to use an adequate method of contraception starting with signing the informed consent through 120 days after the last dose of study medication. Demonstrated adequate organ function as defined in following criteria. All screening labs should be performed within 14 days of enrollment. Note: Subject must not have taken transfusion, hematopoietic agent; granulocyte-colony stimulating factor (G- CSF) etc., and/or oxygen supplementation within 7 days before the screening labs.

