#### 4.5 Stopping Criteria

#### 4.5.1 Patient Withdrawal Criteria

In accordance with applicable regulations, a participant has the right to withdraw from the study, at any time and for any reason, without prejudice to his future medical care.

Withdrawal from the study and therapeutic measures taken shall be at the discretion of the Investigator. A full explanation for the discontinuation from the study should be made in the participant's medical records and in the eCRF.

Premature discontinuation from active study participation may occur at any time due to any of the following reasons:

- Any situation where, in the opinion of the Investigator or the Medical Monitor, continued participation in the study would not be in the best interest of the patient.
- Positive pregnancy test (see Section for procedures to be followed in case of a pregnancy).
- Patient initiates other anti-cancer therapy. The anti-cancer therapy will be documented in the medical record and eCRF.
- Patient is unable or unwilling to comply with study procedures.
- Patient is lost to follow-up.
- Patient withdraws consent.
- Request by a Health Authority.
- Termination of the study by the study investigator(s).
- Progressive neoplastic disease, unless the Investigator feels this may be pseudoprogression, in which case the patient may remain on study until the next evaluation for extent of disease.

The reason(s) for premature study discontinuation/withdrawal should be reported in the eCRF and within the source documents along with the date of withdrawal. AEs should be documented according to Section 7.0 Adverse Events.

For all patients who discontinue, a Final Visit will be performed within  $28 \pm 5$  days after the last IP administration. If a participant is withdrawn because of an AE, the Investigator must arrange for the participant to have appropriate follow-up care until the AE is resolved or has stabilized. Unresolved AEs will be followed until the last scheduled follow-up visit or until the Investigator determines that further follow-up is no longer indicated. Investigators should attempt to collect the survival information as dictated in section 6.1.3.

Patients who discontinue the active study participation will not be replaced.

Any enrolled patients who are discontinued before study dosing will be documented as screen failures in the eCRF and replaced. No follow-up is required for these patients.

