# 5.2.4 Dose Delay and Adjustment

# Pembrolizumab

Pembrolizumab is given at a flat dose of 200 mg IV every 3 weeks, per institutional guidelines. There are no dose modifications to this treatment.

Adverse events (both non-serious and serious) associated with pembrolizumab exposure may represent an immunologic etiology. These adverse events may occur shortly after the first dose or several months after the last dose of treatment. Pembrolizumab must be withheld for drug-related toxicities and severe or life-threatening AEs as per Table 2 below. See Section 5.2.2.6 and Events of Clinical Interest Guidance Document for supportive care guidelines, including use of corticosteroids.

**Table 2**. Dose Modification Guidelines for Pembrolizumab -Related Adverse Events (as per package insert).

Toxicit y	Hold Treatme nt For Grade	Timing for Restarting Treatment	Discontinue Subject from Study Treatment
Diarrhe a/Coliti s	2-3	Toxicity resolves to Grade 0- 1.	Toxicity does not resolve within 12 weeks of last dose or inability to reduce corticosteroid to 10 mg or less of prednisone or equivalent per day within 12 weeks.

Toxicit y	Hold Treatme nt For Grade	Timing for Restarting Treatment	Discontinue Subject from Study Treatment
	4	Permanently discontinue	Permanently discontinue
AST, ALT,	2	Toxicity resolves to Grade 0-1	Toxicity does not resolve within 12 weeks of last dose.
or Increas ed Bilirubi n	3-4 Permanently discontinue		Permanently discontinue
Type 1 diabete s mellitus (if new onset) or Hyperg lycemia	T1DM or 3-4	Hold pembrolizumab for new onset Type 1 diabetes mellitus or Grade 3-4 hyperglycemia associated with evidence of beta cell failure.	Resume pembrolizumab when patients are clinically and metabolically stable.
Hypoph ysitis	2-3	Toxicity resolves to Grade 0-1	Toxicity does not resolve within 12 weeks of last dose or inability to reduce corticosteroid to 10 mg or less of prednisone or equivalent per day within 12 weeks.
	4	Permanently discontinue	Permanently discontinue
Hypert hyroidi sm	3	Toxicity resolves to Grade 0-1	Toxicity does not resolve within 12 weeks of last dose or inability to reduce corticosteroid to 10 mg or less of prednisone or equivalent per day within 12 weeks.
	4	Permanently discontinue	Permanently discontinue
Hypoth yroidis m	2-4	Therapy with pembrolizumab can be continued while treatment for the thyroid disorder is instituted	Therapy with pembrolizumab can be continued while treatment for the thyroid disorder is instituted.

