- h. End of study will occur 28 days (+/- 5 days) following study removal, disease progression, or following 2 years on treatment. Patients may still be followed for survival for up to 96 weeks from study start.
- i 12-lead ECG will be recorded after the patient has rested for 5 minutes
- j. Tumor biopsy may be needed during screening phase for PD-L1 testing if there is no archival tissue available.
- k. Only needed, if screening CBC and chemistry done more than 7 days prior to first cycle of pembrolizumab.
- 1. OBP-301 will be administered every 2 weeks (-2 business day/+5 business day window). If the window is used, the following doses should be
- administered following the same window, ensuring at least 12 days between each OBP-301 administration.
- m. Pregnancy test for screening should be done within 7 days of Day 1.
- n. A CBC and CMP should be obtained within 10 days of OBP injection, if not already performed.
- o. OBP-301 and Pembrolizumab should not be administered on the same day.

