#### 8.3 Handling of Missing Values and of Values outside the Detection Limits

Missing values will not be imputed. All missing values will be reported in the listings as either "missing" or as the justification for the value being missing (e.g., "ND" [test not done] or "BQL" [below quantitation limit], where appropriate.

While efforts will be made to avoid incomplete or missing data, in rare cases the AE date could be incomplete or missing. If this happens, incomplete or missing dates will be imputed. For the calculation of AE duration and AE onset from dosing, missing AE dates will be imputed using a conservative approach. This approach will assume that the AE is treatment emergent where insufficient date information exists to determine if the AE occurred before or after dosing, except where year is missing. If the year is also missing then it will be assumed that the start is before the start of the study.

Imputed onset dates of AEs will be checked to ensure they occur after the first study day and before the resolution date. Imputed resolution dates will be checked to ensure they occur after the onset date and before date of last study visit (where AE is not flagged as ongoing).

Descriptive statistics for demographics, body weight, vital signs, and ECG data will be calculated from actual data only, with the number of actual data points used for the calculation of the summary statistics reported.

For censored safety lab data (i.e., hematology, clinical chemistry and urinalysis results that are outside the limit of quantification) the actual values reported by the laboratory (e.g., "< 2" for bilirubin) will be presented in the data listings. For the calculation of summary statistics, safety laboratory data values below the lower limit of quantification (LLOQ) will be set to  $\frac{1}{2}$  the LLOQ.

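### The treatment-emergent AE window has no consistent end once OBP-301 injections stop, and the missing-year rule for AE onset is anti-conservative and contradicts its own check

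*Combined protocol and SAP*

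**What the plan says.** **Window.** Section 7.2.3 gives the treatment-emergent period: "Treatment-emergent AEs will be evaluated from the time of injecting with IP until the Final Visit". The synopsis ties IP to one agent: "OBP-301, the investigational product (IP) is formulated in" (the composition follows). Sections 4.5.1 and 6.1.4 set a Final Visit for patients who discontinue. After the figure 28 ± 5, the text of 4.5.1 runs "days after the last IP administration. If a participant is withdrawn because of an AE" and goes on to follow-up care. Section 6.1.2 plans OBP-301 on Days 1, 15, 29 and 43. It allows one further injection two weeks after the fourth, and rechallenge at progression for initial responders. Pembrolizumab is given every 3 weeks until progression (5.2, 6.1.2).

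The Schedule of Events (6.1) has no Final Visit column. Its closing column is End of Study, which footnote h defines: "End of study will occur 28 days (+/- 5 days) following study removal, disease progression, or following 2 years on treatment". Footnote g schedules AE review every 3 weeks from week 10 until then. On pembrolizumab AEs, Section 5.2.4 says: "These adverse events may occur shortly after the first dose or several months after the last dose of treatment".

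**Missing dates.** Section 8.3 describes its imputation of AE dates as conservative and by default treats an AE with insufficient date information as treatment-emergent. It makes one exception: "If the year is also missing then it will be assumed that the start is before the start of the study". Its next paragraph adds: "Imputed onset dates of AEs will be checked to ensure they occur after the first study day".

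**The concern.** Safety of the combination is one of the two primary objectives (2.1), yet the treatment-emergent window is anchored to the agent that stops first. A patient who stays on pembrolizumab can have an AE on active study treatment that, by the literal definition, is not treatment-emergent. Section 5.2.4 itself warns of late immune-related events. The trial is single-arm and open-label, so a window that can be read two ways leaves the choice to be made after the AEs are known.

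The date rule is a separate defect that acts in the same direction. The default for incomplete dates counts the event; the exception for a missing year takes it out of the treatment-emergent set.

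**Working it through.** The plan gives no calendar day for the end of the window, so there is no figure to reproduce. The inputs are its own scheduled days, assuming on-schedule dosing.

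**1. Literal Final Visit** = last OBP-301 day + 28, ± 5.
- Four injections: 43 + 28 = Day 71 (66 to 76).
- Five injections: 43 + 14 = Day 57; 57 + 28 = Day 85 (80 to 90).
- Rechallenge at progression would move it later.

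**2. Pembrolizumab doses inside the window.** The schedule gives Days 4, 25 and 46, then every 21 days, so dose k falls on Day 4 + 21(k − 1).
- By Day 71: Days 4, 25, 46, 67 = 4 doses (3 if the visit falls on Day 66).
- By Day 730: the last is 4 + 21 × 34 = Day 718 = 35 doses.

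**3. Literal window against footnote h.** End of Study = progression day (or Day 730) + 28. Uncovered days = End of Study − 71. The first three rows use multiples of the nine-week imaging interval as illustrative progression days.

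| Event | End of Study | Uncovered days | Uncovered share |
|---|---|---|---|
| Progression Day 63 | 91 | 20 | 20/91 = 22% |
| Progression Day 126 | 154 | 83 | 83/154 = 54% |
| Progression Day 189 | 217 | 146 | 146/217 = 67% |
| 2 years on treatment | 758 | 687 | 687/758 = 91% |

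These are shares of time, not of events. The documents give no AE rate over time, so the number of reclassified AEs cannot be computed.

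**4. Where the treatment-emergent label is used.** It appears in 7.2.3 and 8.3. Section 8.7.2 tabulates and lists all AEs as defined in Section 7, with no treatment-emergent filter. The synopsis tabulates toxicities with exact confidence intervals, also unfiltered. The stopping rule in 8.7.9 applies at any time. Section 7.2.5 requires SAEs to be reported throughout the study, or within 28 days of IP, whatever their relatedness.

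**5. Missing-year rule against its neighbours.**
- An onset placed before the study cannot pass the check that imputed onsets fall after the first study day.
- Under 7.2.3, non-serious events between consent and the Day 1 injection go to medical history, and 7.2.1 and 7.2.2 start the AE log after Day 1. A non-serious AE on that log is therefore unlikely to have a pre-study onset.
- SAEs are reported from consent, so an SAE with no year could truly precede the first injection.
- Section 8.3 imputes dates for AE duration and onset from dosing. The event keeps its place in the all-AE tables and listing; what changes is its treatment-emergent status and onset timing.

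**The case against.** The strongest reply is that Day 71 is only one reading, and an unworkable one. The Final Visit is defined only for patients who discontinue, and someone who stops pembrolizumab at month 12 cannot attend a visit dated 28 days after an injection on Day 43. If Final Visit is taken to mean End of Study, nothing is truncated. This stands as a reason not to treat Day 71 as settled. It does not remove the problem: the text of 4.5.1 and 6.1.4 says otherwise, and patients who have not discontinued have no defined Final Visit at all.

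A reader might also infer that the primary safety analysis undercounts AEs. The documents do not support that. Collection runs to End of Study, 8.7.2 has no treatment-emergent filter, the stopping rule has no window, and 7.2.5 already covers SAEs during the study. Nor is an AE with a missing year dropped from the analysis: it stays in the all-AE tables and listing.

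Finally, the two-year patient is the extreme case in a third- or fourth-line population. With progression at the first scan, the uncovered share is 22%.

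**Conclusion.** Two wording defects stand.

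First, the definitions of the Final Visit and End of Study conflict. Read literally, the treatment-emergent window closes about 28 days after the last OBP-301 injection while pembrolizumab continues. The uncovered time runs from 20 days (progression at Day 63) to 687 days (2 years on treatment), assuming four on-schedule injections and no rechallenge. An undercount would arise only in analyses restricted to treatment-emergent AEs under that reading. Section 8.1 defers full detail to a statistical analysis plan, and Section 8 does not say whether any such restriction will apply.

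Second, the missing-year rule runs against the section's stated conservative aim, contradicts the onset check beside it, and is implausible for non-serious AEs. Section 8.3 expects incomplete AE dates to be rare, and the number with no year cannot be estimated.

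Both rules would misclassify events if followed as written, and both are worth correcting before analysis. Neither shows that the safety results will be biased.

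**What to change.** - Reconcile 4.5.1, 6.1.4, 7.2.3 and footnote h to one closing visit that applies to every treated patient.
- In 7.2.3, run the treatment-emergent window from the first OBP-301 injection to the later of the End of Study visit (footnote h) and 28 days after the last dose of either OBP-301 or pembrolizumab. Last dose plus 28 days alone would not do: it does not match footnote h, and because Table 2 in 5.2.4 contemplates holds of up to 12 weeks from the last dose, it could close while scheduled AE review continues.
- In 7.2.5, keep the existing coverage of SAEs throughout the study.
- In 8.3, treat an AE with a missing year as treatment-emergent unless other data show onset before the first injection.

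The cost is wording only, since AE review is already scheduled every 3 weeks to End of Study. Treatment-emergent AE rates may be slightly higher. The revised window still will not reach events that begin months after both the last dose and End of Study.
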